5.1 Overall Study Design and Plan: Description

This is a Phase 2, multicenter, open-label study designed to evaluate the tolerability and efficacy of navitoclax alone or in combination with ruxolitinib in subjects with primary or secondary myelofibrosis (PPV-MF, PET-MF). Subjects enrolled in Cohort 1a must have received ruxolitinib therapy for at least 12 weeks and currently be on a stable dose of ≥ 10 mg twice daily of ruxolitinib. For Cohort 1b subjects must have received treatment with ruxolitinib. For Cohort 2, subjects must have received prior treatment with a JAK-2 inhibitor. For Cohort 3, subjects must not have received prior treatment with a JAK-2 inhibitor or BET inhibitor.

Approximately 174 subjects at approximately 135 sites globally will be enrolled in the following cohorts:

- Cohort 1a: 34 subjects (fully enrolled as of 10 April 2019)
- Cohort 1b: approximately 80 subjects will be enrolled to ensure enrollment of approximately 70 subjects with prior exposure to ruxolitinib.
- Cohort 2: approximately 30 subjects
- Cohort 3: approximately 30 subjects

The study is designed to meet scientific and regulatory objectives without enrolling an undue number of subjects in alignment with ethical considerations. All efforts will be made to adhere to these specific enrollment numbers; however, it might not be ethical to deny treatment to subjects in Screening as they may have undergone study related procedures. Subjects that are enrolled and do not meet the inclusion criteria as outlined in Section 5.2 may be replaced at the discretion of the Sponsor.

The study will consist of the following:

Screening: Study assessment performed prior to enrollment;

- **Treatment:** Study assessments performed from first dose through the Treatment Completion Visit (TCV);
- Follow-up:
 - Safety Follow-up: approximately 30 days following TCV to assess adverse events
 - **Post-Treatment Follow-up:** Every 12 weeks after the TCV until disease progression is documented or until another therapy for MF is initiated
 - **Survival:** Every 6 months follow-up for survival status and collection of post-treatment cancer therapy details

[figure not shown]
Screening

Unless otherwise specified, Screening assessments must be performed within 28 days prior to first dose of navitoclax. For subjects enrolled in Cohorts 1b and 3, the screening period should be long enough to ensure there is at least 7 days to collect the daily MFSAF v4.0 prior to Day 1.

Treatment

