5.2.1 Inclusion Criteria

A subject will be eligible for study participation if he/she meets the following criteria:

- 1. Subject must voluntarily sign and date an informed consent, approved by an Independent Ethics Committee (IEC)/Institutional Review Board (IRB), prior to the initiation of any Screening or study-specific procedures.
- 2. Subject must be ≥ 18 years of age.
- 3. Subjects with documented diagnosis of Primary MF, PPV-MF, or PET-MF as defined by the World Health Organization classification.
- 4. Subjects classified as intermediate-2 or high-risk MF, as defined by the Dynamic International Prognostic Scoring System (DIPSS).

- 5. Subject must be ineligible due to age, comorbidities, or unfit for unrelated or unmatched donor transplantation or unwilling to undergo stem cell transplantation at time of study entry.
- 6. ECOG 0, 1, or 2.
- 7. Cohort 1a only: Subject must have received ruxolitinib therapy for at least 12 weeks and be on a stable dose of ≥ 10 mg twice daily of ruxolitinib for ≥ 8 weeks prior to the 1st dose of navitoclax.

Note: Subjects with ruxolitinib dose reductions within 8 weeks prior to study enrollment may be considered on a stable dose if stable at that decreased dose of ruxolitinib for ≥ 2 weeks prior to the 1^{st} dose of navitoclax. If the dose reduction was due to thrombocytopenia, the platelets must be confirmed to be stable by a repeat laboratory test.

- 8. **Cohort 1b only:** Subject must have received treatment with ruxolitinib and meet at least one of the following criteria:
 - a. Prior or current treatment with ruxolitinib for ≥ 24 weeks with lack of efficacy defined as a lack of spleen response (refractory) or a loss of spleen or symptom response (relapsed)
 - b. Prior or current treatment with ruxolitinib for < 24 weeks with documented disease progression while on ruxolitinib as defined by any of the following:
 - i. Appearance of new splenomegaly that is palpable to at least 5 cm below the left costal margin (LCM) in subjects with no evidence of splenomegaly prior to the initiation of ruxolitinib.
 - ii. $A \ge 100\%$ increase in the palpable distance below the LCM in subjects with measurable spleen distance 5 to 10 cm prior to the initiation of ruxolitinib.
 - iii. $A \ge 50\%$ increase in the palpable distance below the LCM in subjects with measurable spleen distance > 10 cm prior to the initiation of ruxolitinib.

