8.3.2.4 Deaths

The number of subject deaths will be summarized 1) for deaths occurring while the subject was still receiving study drug in this study, 2) for deaths occurring off treatment within 30 days after the last dose of study drug, and 3) for all deaths in this study regardless of the number of days after the last dose of study drug.

8.3.2.5 **Laboratory Data**

Where applicable, laboratory values will be categorized according to the NCI CTCAE version 4.03 grades, and shifts from baseline grade to post-baseline maximum grades will be assessed.

Detailed listings of data for subjects experiencing NCI CTCAE Grade 3 to 4, blood chemistry and hematology values will be provided. All measurements collected, regardless of the number of days after the last dose of study drug, will be included in these listings.

8.3.2.6 **Vital Signs**

Detailed listings of data for subjects experiencing potentially clinically significant vital sign values according to the AbbVie-defined criteria for vital sign values will be provided. All measurements collected, regardless of the number of days after the last dose of study drug, will be included in these listings.

Approximately 174 subjects in total will be enrolled in this study. Point estimate and exact 95% confidence interval of SVR_{35w24} rate corresponding to expected observed number of subjects with SVR_{35w24} are presented in Table 5.

Table 5. Point Estimates and 95% CI of Rate of SVR_{35w24} Corresponding to Observed Number of Subjects with SVR_{35w24}

			Point Estimate	Exact 95% CI		Half Width of CI
-		Number of Subjects with SVR _{35w24}	(SVR _{35w24} Rate) (%)	Lower Limit (%)	Upper Limit (%)	
1a	34	16	47.06	29.78	64.87	17.55
1a	34	18	52.94	35.13	70.22	17.55
1a	34	20	58.82	40.70	75.35	17.33
1a	34	22	64.71	46.49	80.25	16.88
1b	70	32	45.71	33.74	58.06	12.16
1b	70	34	48.57	36.44	60.83	12.19
1b	70	36	51.43	39.17	63.56	12.19
1b	70	38	54.29	41.94	66.26	12.16
2 or 3	30	12	40.00	22.66	59.40	18.37
2 or 3	30	14	46.67	28.34	65.67	18.67
2 or 3	30	16	53.33	34.33	71.66	18.67
2 or 3	30	18	60.00	40.60	77.34	18.37

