Based on the table above, this study with proposed sample sizes will provide a reasonable precise estimate of the proportion of subjects with SVR_{35w24} for each cohort. According to Section 8.1, Set 1 is expected to consist of subjects from Cohorts 1a and 1b. Also, if true probability of experiencing a serious adverse event (SAE) due to the study treatment is 10%, then the probability of observing at least one SAE in 34 subjects is more than 97% in Cohort 1a; the probability of observing at least one SAE in 80 subjects is more than 99% in Cohort 1b; the probability of observing at least one SAE in 30 subjects is more than 95% in Cohort 2 or 3, respectively. Therefore, from safety assessment prospective the proposed sample size is adequate.

9.0 **Ethics**

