# 2.2 Study Design Overview

[figure not shown]
This is a Phase 2, multicenter, open-label study designed to evaluate the tolerability and efficacy of navitoclax alone or in combination with ruxolitinib in subjects with primary or secondary myelofibrosis (PPV-MF, PET-MF). Subjects enrolled in Cohort 1a must have received ruxolitinib therapy for at least 12 weeks and currently be on a stable dose of  $\geq 10$  mg BID of ruxolitinib. For Cohort 1b subjects must have received treatment with ruxolitinib for at least 24 weeks and currently on stable dose of  $\geq 10$  mg BID of ruxolitinib or had < 24 weeks of ruxolitinib with evidence of disease progression. For Cohort 2, subjects must have received prior treatment with a JAK-2 inhibitor. For Cohort 3, subjects must not have received prior treatment with a JAK-2 inhibitor, BH3 mimetic or BET inhibitor.

Approximately 174 subjects at approximately 135 sites globally will be enrolled in the following cohorts:

- Cohort 1a: 34 subjects
- Cohort 1b: approximately 80 subjects will be enrolled to ensure approximately 70 subjects with prior Ruxolitinib exposure.
- Cohort 2: approximately 30 subjects
- Cohort 3: approximately 30 subjects

Figure 1 is the study schema per protocol.

Figure 1. Study Schematic

Subjects will continue their treatment until end of clinical benefit, unacceptable toxicity or subject meets other protocol criteria for discontinuation (whichever occurs first). All subjects will have a treatment completion visit (TCV) performed when treatment is discontinued.

Response and progression will be assessed by the Investigator based on the International Working Group-Myeloproliferative Neoplasms Research and Treatment and European Leukemia Net (IWG-MRT/ELN). Spleen volume will be assessed independently by a central imaging vendor and interpretations will be transmitted to investigators, as available, and will be utilized in determining response and progression.

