## 2.4 Sample Size Determination

The primary endpoint for each Cohort of the study is SVR35W24 (at least 35% reduction in spleen volume by MRI/CT at Week 24 from baseline). Approximately 174 subjects in total will be enrolled in this study across all Cohorts. Point estimate and exact 95% confidence interval of SVR35W24 rate corresponding to observed number of subjects with SVR35W24 are presented in Table 1 for each Cohort.

Table 1. Point Estimates and 95% CI of Rate of SVR35W24 Corresponding to Observed Number of Subjects with SVR35W24

	Sample Subject		cts with (SVR 35w24 Rate)	Exact 95% CI		
Cohort		Number of Subjects with SVR 35W24		Lower Limit (%)	Upper Limit (%)	Half Width of CI
1a	34	16	47.06	29.78	64.87	17.55
1a	34	18	52.94	35.13	70.22	17.55
1a	34	20	58.82	40.70	75.35	17.33
1a	34	22	64.71	46.49	80.25	16.88
1b	70	32	45.71	33.74	58.06	12.16
1b	70	34	48.57	36.44	60.83	12.19
1b	70	36	51.43	39.17	63.56	12.19
1b	70	38	54.29	41.94	66.26	12.16
2 or 3	30	12	40.00	22.66	59.40	18.37
2 or 3	30	14	46.67	28.34	65.67	18.67
2 or 3	30	16	53.33	34.33	71.66	18.67
2 or 3	30	18	60.00	40.60	77.34	18.37

The study with 34 subjects in Cohort 1a, 70 subjects in Cohort 1b, 30 subjects in Cohort 2 and 30 subjects in Cohort 3 showed in the above table, respectively, a reasonable precision for estimate of SVR35W24. Also, if true probability of experiencing a serious

adverse event (SAE) due to the study treatment is 10%, then the probability of observing at least one SAE in 34 subjects is more than 97% in Cohort 1a; the probability of observing at least one SAE in 80 subjects is more than 99% in Cohort 1b; the probability of observing at least one SAE in 30 subjects is more than 95% in Cohort 2 and 3, respectively. Therefore, from safety assessment prospective the proposed sample size is adequate.

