# 4.0 Analysis Populations

[figure not shown]
In this study, study treatment is navitoclax + ruxolitinib (Cohort 1a, 1b and 3) or navitoclax alone (Cohort 2). Unless otherwise noted, study drug refers to navitoclax and ruxolitinib for combination therapy (Cohort 1a, 1b, and 3); and navitoclax for mono therapy (Cohort 2). Cohort 1 refers to Cohort 1a and Cohort 1b together.

The following sets will be used for analyses:

Full Analysis Set (FAS) includes all enrolled subjects who received at least one dose of navitoclax. The FAS will be used for all demographic/baseline analyses. Unless otherwise specified, the FAS is also the analysis population for the primary and the secondary endpoints.

The Safety Analysis Set includes all enrolled subjects who received at least one dose of navitoclax. The safety analysis set will be used for all safety analyses, unless otherwise specified.

The pharmacokinetics (PK) analysis set includes all the enrolled subjects who received at least one dose of navitoclax and have at least one post-dose PK assay results. The PK set will be used for PK analyses.

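### Cohort 1b precision is stated for 70 subjects, but the planned primary analysis uses all of about 80 dosed subjects, and the reason given for enrolling 80 conflicts with the eligibility criteria

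*Protocol*

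**What the plan says.** Protocol Section 5.1 sets the Cohort 1b target: "approximately 80 subjects will be enrolled to ensure enrollment of approximately 70 subjects with prior exposure to ruxolitinib". SAP Section 2.2 repeats it: "approximately 80 subjects will be enrolled to ensure approximately 70 subjects with prior Ruxolitinib exposure".

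Eligibility is stricter than that sentence implies. Inclusion criterion 8 in protocol Section 5.2.1, which applies to Cohort 1b only, reads "Subject must have received treatment with ruxolitinib and meet at least one of the following criteria". Section 5.1 also makes earlier ruxolitinib treatment a condition for the cohort, and SAP Section 2.2 describes only ruxolitinib-treated subjects.

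The two documents use two different numbers for the cohort:

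- **Efficacy precision, 70.** The Cohort 1b rows of protocol Table 5 and SAP Table 1 use 70. SAP Section 2.4 draws its conclusion on that basis: "The study with 34 subjects in Cohort 1a, 70 subjects in Cohort 1b, 30 subjects in Cohort 2 and 30 subjects in Cohort 3".
- **Safety and total, 80.** The protocol's sample size text says "the probability of observing at least one SAE in 80 subjects is more than 99% in Cohort 1b", and also "Approximately 174 subjects in total will be enrolled in this study", a total that counts 80 in Cohort 1b.

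On the analysis set, SAP Section 4.0 says "Full Analysis Set (FAS) includes all enrolled subjects who received at least one dose of navitoclax". SAP Sections 8.1 and 8.3.1 make this set primary for SVR35 at Week 24, present efficacy by cohort, and count subjects without a usable Week 24 spleen volume as non-responders. The only sets defined are the Full Analysis Set, the Safety Analysis Set and the PK set. The subgroups named in SAP Section 8.7 are type of MF, DIPSS risk and age.

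**The concern.** This trial makes no formal test. Its sample size is justified by the width of the confidence interval in each cohort, so the table should describe the interval that the analysis will produce. For Cohort 1b it does not: the table uses 70 and the analysis set holds about 80. Because missing Week 24 data count as non-response, dropout cannot bring the denominator down to 70.

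The enrolment sentence adds a question about who is being estimated. If 80 subjects are needed to secure 70 with earlier ruxolitinib, some would lack it. That matters because there is no control arm. Protocol Section 5.6 attributes benefit to navitoclax on the ground that further improvement is not expected after 12 weeks of ruxolitinib or another JAK-2 inhibitor. The same section says that about 40% of patients reach a 35% spleen volume reduction on ruxolitinib, typically within 12 to 24 weeks. Under Section 5.1, Cohort 1b subjects who are not on ruxolitinib at screening start it on Day 1. For a subject never exposed before, a Week 24 response could come from ruxolitinib, and the Section 5.6 argument would not apply.

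**Working it through.** **1. Reproduce the stated figures.** The method is the exact two-sided 95% Clopper-Pearson interval (protocol Section 8.3.1; SAP Section 8.3.2). For x responders out of n, the lower limit is the 0.025 quantile of Beta(x, n − x + 1), the upper limit is the 0.975 quantile of Beta(x + 1, n − x), and the half-width is (upper − lower)/2.

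| x/n | Rate (%) | 95% CI (%) | Half-width |
|---|---|---|---|
| 32/70 | 45.71 | 33.74 to 58.06 | 12.16 |
| 34/70 | 48.57 | 36.44 to 60.83 | 12.19 |
| 36/70 | 51.43 | 39.17 to 63.56 | 12.19 |
| 38/70 | 54.29 | 41.94 to 66.26 | 12.16 |

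These match both tables to two decimals, as do the rows for the other cohorts.

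**2. Establish which N the rest of the plan uses.** 34 + 80 + 30 + 30 = 174, the stated total; with 70 in Cohort 1b it would be 164. The SAE probability is 1 − 0.9^80 = 99.98%. With 70 it would be 99.94%, so the choice of N has no bearing on that claim, but it shows that 80 is the cohort size.

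**3. Look for an analysis with n = 70.** The by-cohort Full Analysis Set gives about 80. Pooling Cohorts 1a and 1b, as in Set 1 of protocol Section 8.1, gives 34 + 80 = 114. No set or named subgroup is defined by earlier ruxolitinib exposure. None of these is 70.

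**4. Recompute at n = 80, at similar rates.**

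| x/n | Rate (%) | 95% CI (%) | Half-width |
|---|---|---|---|
| 37/80 | 46.25 | 35.03 to 57.76 | 11.37 |
| 39/80 | 48.75 | 37.41 to 60.19 | 11.39 |
| 41/80 | 51.25 | 39.81 to 62.59 | 11.39 |
| 43/80 | 53.75 | 42.24 to 64.97 | 11.37 |

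The difference is 12.19 − 11.39 = 0.80 points, in the direction of more precision than stated. At a rate of 30% the half-widths are 11.26 (21/70) and 10.51 (24/80), a difference of 0.75.

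**5. Bound the effect on the estimate if unexposed subjects were dosed.** The count of 10 is inferred from 80 − 70; neither document states it. With exposed rate p and unexposed rate q, the pooled rate is (70p + 10q)/80, so the shift from p is 0.125 × (q − p).

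- Extremes at 36/70: if none of the 10 respond, 36/80 = 45.0%, a shift of −6.4 points. If all respond, 46/80 = 57.5%, a shift of +6.1 points.
- An illustration from the protocol's own figures: take p from Cohort 1a at 9/34 = 26.5% (Section 3.4) and q = 40% (Section 5.6). The pooled rate is (70 × 0.265 + 10 × 0.40)/80 = 28.2%, a shift of +1.7 points. With p = 29%, the Week 24 rate given in Section 5.6, the shift is 0.125 × (0.40 − 0.29) = +1.4 points.

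Using these rates for Cohort 1b is an assumption.

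**The case against.** The strongest objection is that the other 10 subjects may not exist. Every current eligibility statement for Cohort 1b requires earlier ruxolitinib, criterion 10 bars any other JAK-2 inhibitor, and no text admits an unexposed subject. If criterion 8 holds for all 80, the population is the intended one and only the table is out of step. This stands. A reader might infer that the primary estimate is known to mix in 10 subjects outside the question, and the documents do not support that. Being off ruxolitinib at screening, which Section 5.1 allows, does not mean never having received it.

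It does not settle the matter, however. If all 80 are exposed, the stated reason for enrolling 80 has no meaning. The SAP also expects subjects enrolled under other amendments: Section 7.2.1 defines baseline TSS by amendment, and Section 8.7 lists a DIPSS intermediate-1 subgroup although criterion 4 now admits only intermediate-2 and high risk. Nor can the step from 70 to 80 be read as a dropout allowance. 70/(1 − 0.125) does equal 80, but the text gives exposure as the reason and states no dropout rate.

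A second objection is that 0.8 points changes no decision in an estimation-only study with approximate enrolment numbers. That also stands: the sample size is not undermined, and a reader who infers that precision is overstated has the direction wrong.

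A third concerns the remedy. One might want the exposed subjects to be the primary set. In an open-label study whose data the sponsor reviews without an independent committee (SAP Section 11.1), all dosed subjects with missing counted as non-response is the set harder to bias. The SAP history also shows an efficacy evaluable set added in version 2.0 and removed in 3.0. This argues for keeping the Full Analysis Set primary.

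Finally, the subgroup list in SAP Section 8.7 is open-ended, and the baseline tables in Section 7.3 include duration of earlier ruxolitinib and response to it. An exposure split is therefore permitted and any unexposed subjects could be identified, but the split is not pre-specified.

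**Conclusion.** The point holds as a mismatch between the precision table and the planned analysis, together with an unresolved contradiction between the enrolment sentence and criterion 8. The stated half-width of 12.16 to 12.19 points belongs to no planned Cohort 1b analysis; at n = 80 and similar rates it is 11.37 to 11.39. The error is small and conservative. This assumes that about 80 subjects are dosed, as planned.

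Whether the estimate refers to the wrong population cannot be settled from the documents. Any shift depends on an inferred number of unexposed subjects and on assumed response rates. With 10 such subjects it lies between −6.4 and +6.1 points when the exposed rate is 36/70, and is about +1.4 to +1.7 points in the illustration from the protocol's own figures. If all 80 were previously treated with ruxolitinib, it is zero.

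**What to change.** 1. Keep the Full Analysis Set as the primary set for Cohort 1b, and say in SAP Section 8.3 that the denominator is all dosed Cohort 1b subjects, about 80.
2. Restate the Cohort 1b rows of SAP Table 1, protocol Table 5 and the matching synopsis table at n = 80, for example 41/80 = 51.25%, 95% CI 39.81 to 62.59, half-width 11.39. Change the 70 in the text of SAP Section 2.4 to match.
3. Reconcile the enrolment sentence with criterion 8 wherever it appears in the protocol and SAP. State who the other 10 or so subjects are, or drop the distinction if every subject is exposed.
4. If any dosed Cohort 1b subject has no earlier ruxolitinib exposure, pre-specify a supportive SVR35 Week 24 estimate in the exposed subjects only (about 70, half-width about 12.2 at rates near 50%). Fixing it before analysis removes the option of choosing between 70 and 80 after open-label results are seen.

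The cost is wording, the restated rows and at most one additional output table. No new data are needed and the primary analysis does not change.

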During treatment, all assessments must be performed on the day of the specified visit unless a time window is specified in the schedule of assessments (Appendix C). Refer to Section 3.6 for study visit modifications.

Subjects will continue their treatment until end of clinical benefit, unacceptable toxicity or subject meets other protocol criteria for discontinuation (whichever occurs first). All subjects will have a TCV performed when treatment is discontinued.

Response and progression will be assessed by the Investigator based on the modified International Working Group-Myeloproliferative Neoplasms Research and European Leukemia Net (IWG-MRT/ELN) and as noted in Appendix E.²⁴ Spleen volume will be assessed by an independent central review and interpretations will be transmitted to investigators, as available, and will be utilized in determining response and progression. The evaluation of fibrosis grading and reticulin staining grading may be assessed independently by a central pathologist. Independent interpretations of bone marrow samples are not planned to be transmitted to investigators. Details regarding the determination of clinical response and disease progression are provided in Appendix E.

Follow-Up

Safety Follow-Up: All subjects will have one Safety Follow-up visit approximately 30 days following TCV.

Post-Treatment Follow-Up: For subjects who discontinue study treatment for reasons other than disease progression, a Post-Treatment Follow-up visit will be performed approximately 12 weeks following TCV, then every 12 weeks thereafter to assess disease

status until criteria are met for discontinuation from study (e.g., disease progression, initiation of post-treatment cancer therapy, or subject refusal of post-treatment follow-up visits).

Once disease progression is confirmed or the subject begins a post-study treatment for MF other than the continuation of ruxolitinib (Cohorts 1a, 1b or 3), the subject will enter the Survival Follow-up phase.

Survival Follow-Up: Survival Follow-up will then be performed approximately every 6 months for up to 5 years after TCV (provided informed consent has not been withdrawn for collection of such information). Survival information (e.g., date and cause of death, details of post-treatment cancer therapies including response and progression) may be collected via telephone calls (e.g., to subject or family member), clinic visits, and/or public database searches.

5.2 **Selection of Study Population**

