5.4 Removal of Subjects from Therapy or Assessment

5.4.1 **Discontinuation of Individual Subjects**

Each subject has the right to withdraw from the study (study treatment and/or follow-up) at any time. In addition, the Investigator may discontinue a subject from treatment at any time for any reason if the Investigator considers it necessary, including the occurrence of an adverse event or noncompliance with the protocol.

During the COVID 19 pandemic, it has been necessary to employ mitigation strategies to enable the investigator to ensure subject safety and continuity of care. Acceptable mitigation strategies are identified and included within this protocol.

Each subject will be withdrawn from study treatment (as applicable) if any of the following occur:

- The subject has disease progression as defined in Appendix E, and the Investigator feels the subject is no longer benefiting from treatment.
- The subject requires alternative therapy for treatment of MF.
- The subject experiences treatment toxicity which, in the Investigator's opinion, prohibits further therapy or the Investigator believes it is otherwise in the best interest of the subject.
- Significant subject noncompliance with study drug administration, study procedures or study requirements.
- Subject becomes pregnant or begins breastfeeding.
- The subject decides to withdraw consent of being treated by study treatment for any reason.
- Any other medical reason that AbbVie or the study Investigator deems appropriate.

Discussion with the TA MD/SD is recommended before discontinuing a subject from the study for any reason other than described above to ensure all acceptable mitigation steps have been evaluated.

In the event that a subject discontinues study treatment, the reason(s) for the discontinuation and the primary reason will be recorded and a TCV will be performed as soon as possible after discontinuation from study treatment.

If a subject is discontinued from study treatment or the study with an ongoing adverse event, the Investigator will attempt to provide follow-up until a satisfactory clinical resolution of the adverse event is achieved.

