A Safety Follow-Up Visit should be performed for all subjects approximately 30 days following last dose of navitoclax. If the TCV was conducted ≥ 30 days after last dose of navitoclax, the Safety Follow-Up visit does not need to be performed. If the subject refuses or is unable to attend the Safety Follow-Up Visit, this should be noted in the subject's source documentation.

In the event that a positive result is obtained on a pregnancy test for a subject or a subject reports becoming pregnant during the study, the administration of the study drug must be discontinued immediately. The Investigator must report a pregnancy within 1 working day of the site being aware to one of the AbbVie representatives listed in Section 6.1.5.

Subjects who permanently discontinue study treatment within the first 28 days on study may be replaced at the Sponsor's discretion.

5.4.2 **Termination of Entire Study**

AbbVie may terminate this study prematurely, either in its entirety or a specific cohort of the study or at any study site, for reasonable cause provided that written notice is submitted in advance of the intended termination. The investigator may also terminate the study at his/her site for reasonable cause, after providing written notice to AbbVie in advance of the intended termination. Advance notice is not required by either party if the study is stopped due to safety concerns. If AbbVie terminates the study for safety reasons, AbbVie will immediately notify the investigator by telephone and subsequently provide written instructions for study termination.

If, in the judgment of the investigator and AbbVie, the continued exposure to the study drug represents a significant risk to subjects, the study will be stopped. The following procedures for termination will be followed:

- If the Sponsor has decided to prematurely terminate the study or a specific cohort of the study, the Sponsor will promptly notify in writing each Investigator as well as regulatory authorities of the decision and give detailed reasons for the discontinuation.
- Each Investigator must promptly notify the IRB/IEC and give detailed reasons for the termination.
- Each Investigator must promptly notify the enrolled subjects of the premature termination and administer appropriate treatments such as replacement of protocol therapy, if applicable, by other appropriate regimens.

5.5 **Treatments**

5.5.1 **Treatments Administered and Dosing**

Navitoclax

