6.1.4 Adverse Event Collection Period

All adverse events reported from the time of study drug administration until 30 days, following discontinuation of navitoclax administration have elapsed will be collected, whether solicited or spontaneously reported by the subject. In addition, protocol-related serious adverse events and protocol-related non-serious adverse events will be collected from the time the subject signed the study-specific informed consent.

Adverse event information will be collected as shown in Figure 2.

Figure 2. Adverse Event Collection

* Only if considered by the Investigator to be causally related to study-required procedures.

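### Protocol 5.1 and 5.4.1 time the Safety Follow-up visit from different dates, and the 5.1 date can put its values past the SAP's 30-day limit

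*Protocol*

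**What the plan says.** **Visit timing.** Protocol Section 5.1 gives the TCV as the anchor twice. The list of study periods has the Safety Follow-up "approximately 30 days following TCV to assess adverse events", and the Follow-Up text says "All subjects will have one Safety Follow-up visit approximately 30 days following TCV". Section 5.4.1 says instead: "A Safety Follow-Up Visit should be performed for all subjects approximately 30 days following last dose of navitoclax". It adds a waiver that 5.1 lacks: "If the TCV was conducted ≥ 30 days after last dose of navitoclax, the Safety Follow-Up visit does not need to be performed".

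**Timing of the TCV.** Section 5.1 says "All subjects will have a TCV performed when treatment is discontinued", and Section 5.4.1 says "a TCV will be performed as soon as possible after discontinuation from study treatment". Neither fixes a day. Appendix C, Table 6 gives NA as the window for both the TCV and the 30-day safety visit. It schedules hematology, chemistry and vital signs at the safety visit.

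**Analysis limits.** SAP 9.4 (drug-induced liver injury) and 9.5 (vital signs) use values up to 30 days after the last date of study treatment. SAP 7.1 defines that date as the last navitoclax dose. SAP 9.3.1 drops laboratory data collected more than 30 days after the last dose of study treatment, a slightly different phrase. SAP 4.0 describes study treatment as navitoclax plus ruxolitinib in Cohorts 1a, 1b and 3.

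**The concern.** Both sections apply to all subjects, so a site can follow either and be compliant with one and not the other. The choice sets the day of the last scheduled safety contact. Because the SAP limits are exact while the visit has no window, it also decides whether the values from an on-target visit are summarised at all.

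At stake are the end-of-treatment liver chemistry and vital signs and, on one reading of the SAP, the laboratory shift tables. For a subject with a very late TCV, one section requires a visit that the other says is unnecessary.

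**Working it through.** The plan states no figure to reproduce; the check is day arithmetic.

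**Inputs.** Count days from the last navitoclax dose (Day 0). Let d be the day of the TCV. The documents give no value for d.

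**Formulas.**
- On-target visit under 5.1: Day 30 + d.
- On-target visit under 5.4.1: Day 30 if d is below 30; no visit needed if d is 30 or more.
- Kept in the SAP 9.4 and 9.5 summaries if the day is 30 or less.

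| d | 5.1 visit day | Kept under 9.4 and 9.5? | 5.4.1 visit day | Difference (days) |
|---|---|---|---|---|
| 0 | 30 + 0 = 30 | yes | 30 (kept) | 0 |
| 1 | 30 + 1 = 31 | no | 30 (kept) | 1 |
| 7 | 30 + 7 = 37 | no | 30 (kept) | 7 |
| 14 | 30 + 14 = 44 | no | 30 (kept) | 14 |
| 29 | 30 + 29 = 59 | no | 30 (kept) | 29 |
| 30 | 30 + 30 = 60 | no | waived | – |

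The two sections agree only at d = 0. From d = 1 to 29 they differ by exactly d days. From d = 30, 5.1 asks for a visit that 5.4.1 waives. Since the TCV is meant to be prompt, I take 0 to 7 days as an illustrative assumption for d; the on-target 5.1 visit then falls between Day 30 and Day 37.

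**Laboratory shift tables.** Here the anchor itself is uncertain.
- Read through SAP 7.1, the 9.3.1 cut-off runs from the last navitoclax dose and the table above applies unchanged.
- Read through SAP 4.0, it could run from the last ruxolitinib dose in Cohorts 1a, 1b and 3. If ruxolitinib counted as study treatment and stopped r days after navitoclax, the cut-off would be Day 30 + r, and the 5.1 visit would be kept whenever 30 + d ≤ 30 + r, that is, d ≤ r.
- SAP 6.4 classes ruxolitinib taken after the last navitoclax dose as post-study treatment, but only for Cohort 1 (1a and 1b). That supports the navitoclax reading there and leaves Cohort 3 open.
- The case can arise. Protocol 5.1 foresees ruxolitinib continuing in all three combination cohorts: a subject who has not progressed moves to survival follow-up on starting "a post-study treatment for MF other than the continuation of ruxolitinib (Cohorts 1a, 1b or 3".

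**Which anchor fits the rest of the plan.** Protocol 6.1.4 says that adverse events reported from study drug administration "until 30 days, following discontinuation of navitoclax administration have elapsed will be collected". SAP 9.2.2 splits deaths at 30 days after the last navitoclax dose, and SAP 9.2.5.3 ends the transfusion count there. These match 5.4.1.

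**The case against.** The best defence is that 5.4.1 is the operative text on discontinuation, while 5.1 is an overview. The waiver makes sense only with a last-dose anchor, and a prompt TCV makes both sections point to nearly the same day. Both say approximately, so the Day 30/31 boundary bites only for a visit held exactly on target; a late visit under 5.4.1 would be lost as well. All of that stands as a limit on size. It does not remove the conflict: nothing in the protocol ranks 5.4.1 above 5.1, and 5.1 repeats its anchor and applies it to every subject.

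A second point in favour of 5.1 is that a visit on Day 30 + d always covers the full adverse-event collection period, whereas a visit about 30 days after the last dose may come early. That is fair, but it is a reason to choose an anchor deliberately, not to keep two.

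A reader might go further in three ways that the documents do not support.
- **Laboratory data are lost from the shift tables in every cohort.** SAP 4.0 leaves the anchor for 9.3.1 open in the combination cohorts, so this is certain only in Cohort 2.
- **Adverse events are lost.** Events with onset by Day 30 count whatever day the visit is held.
- **Table 6 needs a window such as Day 30 to 37, a rewritten waiver and longer SAP windows.** Aligning the anchor already puts the on-target visit on Day 30, inside the limit. Seven of the eight days in such a window (Days 31 to 37) would lie past the present cut-off and, in Cohorts 1a, 1b and 3, might be days on ruxolitinib alone. These are optional preferences, not corrections of the defect.

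**Conclusion.** The inconsistency is real and minor. Sections 5.1 and 5.4.1 give different anchors, and Table 6 does not resolve them. For d of 1 or more, an on-target 5.1 visit falls outside the liver-injury and vital-sign summaries. For the laboratory shift tables the same holds if the cut-off runs from navitoclax.

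Several things keep the effect small:
- Grade 3 or higher laboratory values are listed regardless of day (Protocol 8.3.2.5 and SAP 9.3.1), as are potentially clinically significant vital signs (Protocol 8.3.2.6).
- TCV and unscheduled values within 30 days of the last dose stay in the summaries.
- In tables of the maximum value, only a subject whose worst value falls at this visit changes category.
- The primary endpoint and the sample size are unaffected.

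The conclusion assumes an on-target visit. The share of subjects affected cannot be computed, because d is not given. Confidence is high for the conflict itself and for SAP 9.4 and 9.5, and lower for the shift tables.

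**What to change.** In the next amendment, change both statements in Protocol 5.1 so that the visit is timed about 30 days after the last navitoclax dose, as in 5.4.1, and add a cross-reference to the 5.4.1 waiver. In SAP 9.3.1, state that the laboratory cut-off runs from the last navitoclax dose, so that it agrees with 9.4, 9.5 and the definition in 7.1.

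An on-target visit then falls on Day 30 for every d below 30 and is kept in all three analyses; for d of 30 or more no visit is needed under either section.

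The cost is two wording changes and a cross-reference in the protocol, which need IEC/IRB approval under Protocol 9.1, and one clarifying sentence in the SAP. No assessment is added. A visit held after Day 30 would still fall outside the summaries, as it does now under 5.4.1.
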